### **12. Dosage and Administration of Study Drugs.**

#### **12.1. Study Drug Administration Overview**

Daratumumab and ibrutinib is to be administered as described in the Schedule of Events Table 1. Each cycle is 28 days. The first visit of a cycle should be 4 weeks after the start of the previous cycle. The start of each cycle may occur +/- 3 days of the scheduled day in order to accommodate the schedule of the site or the subject with Day 1 of each subsequent cycle adjusted accordingly to maintain the 28 day cycle duration. During weeks 1-24 daratumumab will be given weekly or bi weekly +/- 3 days in order to accommodate the schedule of the site or subject. During Screening and prior to daratumumab infusion on C1D1 blood type and screening

should be collected.

#### **12.1.1. Daratumumab Administration**

Daratumumab (16mg/kg) will be administered by IV infusion to subjects initially once weekly for 8 weeks, then every other week for 16 weeks, followed by infusion every 4 weeks thereafter until disease progression, unacceptable toxicity, or completion of 2 years of therapy. Each dose will be calculated based on the subject's actual weight rounded to the nearest kilogram. Dosing will be based off the screening weight unless it changes +/- 10% at which point doses will be recalculated. All infusions will be performed as outpatient visits with vital sign monitoring to occur per institutional infusion guidelines.

#### **12.1.2. Daratumumab Preinfusion Medications**

Preinfusion medications are required for subjects on days they receive daratumumab infusions and will receive the following medications prior to each infusion:

- Acetaminophen 650mg orally no more than 1 hour prior to daratumumab infusion
- Diphenhydramine 25-50mg intravenous or orally 30 minutes prior to infusion.
- Methylprednisolone 100mg intravenous 30 minutes prior to infusion. If patients tolerate the infusion without reactions, a lower dose of 60mg methylprednisolone may be substituted for subsequent infusions.

#### **12.1.3. Daratumumab Postinfusion Medications**

Subjects will be asked to take 20 mg of methylprednisolone or glucocorticoid equivalent dose for 2 days post infusion. Consideration should be given to provide short acting beta adrenergic receptor agonists to provide supportive care should bronchospasm occur after returning home from the clinic. If there are no reactions after 4 doses then post-infusion medications may be waived at the investigator's discretion.

### **12.2. Management of Infusion-Related Reactions**

Trained study staff at the clinic should be prepared to intervene in case of any infusion reactions occurring, and resources necessary for resuscitation (e.g., agents such as epinephrine and aerosolized bronchodilator, also medical equipment such as oxygen tanks, and a defibrillator) must be available. Attention to staffing should be considered when multiple subjects will be dosed at the same time.

If an infusion-related reaction develops, then the infusion should be paused. Subjects who experience adverse events during the infusion must be treated according to the investigator's judgment and best clinical practice. The following guidelines may apply:

- Subjects should be treated with acetaminophen, antihistamine, or corticosteroids. Intravenous saline may be indicated. For bronchospasm, urticaria, or dyspnea, subjects may require antihistamines, oxygen, corticosteroids, or bronchodilators. For hypotension, subjects may require vasopressors.
- In the event of a life-threatening infusion-related reaction (which may include pulmonary or cardiac events), or anaphylactic reaction, daratumumab should be discontinued and no additional daratumumab should be administered to the subject. Aggressive symptomatic treatment should be applied.

If an infusion is paused, then a longer-than-anticipated infusion time may occur. Overnight stays at the hospital because of slow infusion times should not be reported as a serious adverse event. However, if the underlying cause of the delayed infusion time is an adverse event or serious adverse event, then that should be reported as such.

#### **12.2.1. Infusion-Related Events of Grade 1 or Grade 2**

If the investigator assesses an adverse event to be related to the daratumumab infusion, then the infusion should be paused. When the subject's condition is stable, the infusion may be restarted at the investigator's discretion. Upon restart, the infusion rate should be half of that used before the interruption. Subsequently, the infusion rate may be increased at the investigator's discretion.

If the subject experiences a Grade 2 or higher event of laryngeal edema or a Grade 2 or higher event of bronchospasm that does not respond to systemic therapy and does not resolve within 6 hours from the onset, then the subject must be withdrawn from treatment.

#### **12.2.2. Infusion-Related Reactions of Grade 3 or Higher**

For infusion-related adverse events that are Grade 4, the infusion should be stopped and treatment with daratumumab will be discontinued for that subject.

For infusion-related adverse events that are Grade 3, the daratumumab infusion must be stopped, and the subject must be observed carefully until the resolution of the adverse event or until the intensity of the event decreases to Grade 1, at which point the infusion may be restarted at the investigator's discretion. Upon restart, the infusion rate should be half of that used before the interruption. Subsequently, the infusion rate may be increased at the investigator's discretion. If the intensity of the adverse event returns to Grade 3 after restart of the infusion, then the procedure described in this section may be repeated at the investigator's discretion. Should the intensity of the adverse event increase to Grade 3 for a third time, then treatment with daratumumab will be discontinued for that subject.

### **12.3. Ibrutinib Administration**

Ibrutinib 420 mg (1m 420mg tablet) is administered orally once daily. The tablet is to be taken around the same time each day with 8 ounces (approximately 240 mL) of water. The tablet

should be swallowed intact and subjects should not attempt to open capsules or dissolve them in water. During treatment days with daratumumab combination dosing, ibrutinib should be taken 0-2 hours prior to daratumumab with 8 ounces of water.

If a dose is not taken at the scheduled time, it can be taken as soon as possible on the same day with a return to the normal schedule the following day. The subject should not take extra capsules to make up the missed dose. The first dose will be delivered in the clinic on Day 1, after which subsequent dosing is typically on an outpatient basis. Ibrutinib will be dispensed to subjects in bottles at each visit. Unused ibrutinib dispensed during previous visits must be returned to the site and drug accountability records updated at each visit. Returned capsules must not be dispensed to anyone.

#### **12.3.1. Ibrutinib Overdose**

Any dose of study drug administered in excess of that specified in this protocol is considered to be an overdose. Signs and symptoms of an overdose that meet any SAE criterion must be reported as a SAE in the appropriate time frame and documented as clinical sequelae to an overdose.

There is no specific experience in the management of ibrutinib overdose in patients. No maximum tolerated dose (MTD) was reached in the Phase 1 study in which subjects received up to 12.5 mg/kg/day (1400 mg/day). Healthy subjects were exposed up to single dose of 1680 mg. One healthy subject experienced reversible Grade 4 hepatic enzyme increases (AST and ALT) after a dose of 1680 mg. Subjects who ingested more than the recommended dosage should be closely monitored and given appropriate supportive treatment.

#### **12.4. Dose Delays and Dose Modification**

Dose modification of daratumumab is not permitted, but dose delay remains the primary method for managing daratumumab-related toxicities. Ibrutinib and daratumumab therapy should be held until recovery upon the onset of any of the following toxicities:

- Grade 4 hematologic toxicity
- Grade 3 thrombocytopenia with bleeding
- Febrile neutropenia of any grade
- Grade 3 or higher nonhematologic toxicities with the following exceptions:
  - Grade 3 nausea that responds to anti-emetics within 7 days
  - Grade 3 vomiting that responds to anti-emetics within 7 days
  - Grade 3 diarrhea that responds to anti-diarrheal within 7 days
  - Grade 3 fatigue that was present at baseline or that lasts for <7 days.
  - Grade 3 asthenia that was present at baseline or that lasts for less than 7 days after.

Supportive care should be provided, and growth factor support should be applied as outlined in

## Section 5.3.

If the investigator feels the toxicities outlined above, are likely attributed to ibrutinib dosing, daratumumab dosing may continue without being held after discussion with the study monitor. Upon recovery of  $\leq$  Grade 2, ibrutinib dosing should be the initial drug restarted. Daratumumab infusions should restart at least 7 days after ibrutinib dosing has resumed and there has been no recurrence of the toxicity.

### **12.4.1. Daratumumab Dose Delay Management**

If dosing is delayed for either toxicity or other non-toxicity related issue then the following schedule should be followed during the specific phases of daratumumab treatment.

During the induction phase (Cycles 1 and 2) if the dose is delayed  $>3$  days then that week's dose will be considered missed and treatment will commence the following week. If a missed dose occurs during induction, then that dose will not be made up and subjects will remain on schedule.

During the consolidation phase (Cycles 3-6) if a dose is held greater than 1 week, then the next dose given should be the scheduled Day 15 dose.

During the maintenance phase Cycle 7 and beyond if a dose is delayed greater than 2 weeks then it should be resumed with the subsequent cycle on day 1.

### **12.4.2. Ibrutinib Toxicity Management**

For toxicities outlined in Section 12.4 the following dose modifications are to be taken:

- First Occurrence: Withhold ibrutinib until recovery to Grade 1 or less and restart at the original dose level
- Second Occurrence: Withhold ibrutinib until recovery to Grade 1 or less, restart at 280mg/day
- Third Occurrence: Withhold ibrutinib until recovery to Grade 1 or less, restart at 140mg/day
- Fourth Occurrence: Discontinue ibrutinib.

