### **7.3. Exclusion Criteria**

- 1) Subject does not have a recorded IgM level recorded within 3 months prior to ibrutinib initiation.**
- 2) Subject meeting definition of disease progression while on ibrutinib. Subjects with IgM levels  $< 0.7\text{g/dL}$  are given special consideration. Please see inclusion criteria for 2b.**
- 3) Subjects in cohort B experiencing ongoing non hematologic toxicities attributable to ibrutinib  $>$  Grade 1 will be excluded from study entry.**
- 4) Major surgery or a wound that has not fully healed within 4 weeks of enrollment.**
- 5) Evidence of disease transformation at time of enrollment.**
- 6) Waldenstrom's complicated by amyloidosis**
- 7) Known central nervous system lymphoma.**

- 8) History of stroke or intracranial hemorrhage within 6 months prior to randomization.
- 9) Requires anticoagulation with warfarin or equivalent vitamin K antagonists (eg, phenprocoumon).
- 10) Requires chronic treatment with strong CYP3A inhibitors. Subjects that required strong CYP3A inhibitors but completed a course of treatment can be considered for enrollment after a washout period of 14 days prior to study drug administration.
- 11) Requires strong CYP3A inducers. Subjects that required strong CYP3A inducers but completed a course of treatment can be considered for enrollment after a washout period of 14 days prior to study drug administration.
- 12) Patients with history of Chronic Obstructive Pulmonary Disease or Reactive Airway disease must have PFTs with FEV1 calculated. Patients with a  $FEV1 \leq 50\%$  of predicted normal will be excluded.
- 13) Clinically significant cardiovascular disease such as uncontrolled or symptomatic arrhythmias, congestive heart failure, or myocardial infarction within 6 months of Screening, or any Class 3 (moderate) or Class 4 (severe) cardiac disease as defined by the New York Heart Association Functional Classification.
- 14) Vaccinated with live, attenuated vaccines within 4 weeks of randomization.
- 15) Seropositive for human immunodeficiency virus (HIV)

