### **10.2. Medications to be Used with Caution with Ibrutinib**

Ibrutinib is metabolized primarily by CYP3A4. The co-administration with strong CYP3A or moderate CYP3A inhibitors may increase ibrutinib concentrations which may increase the risk of drug-related toxicity. Dose modifications of ibrutinib are recommended when used concomitantly with posaconazole, voriconazole, and moderate CYP3A inhibitors. Avoid concomitant use of other strong CYP3A inhibitors. Avoid grapefruit and seveille oranges.

Avoid concomitant use of strong CYP3A inducers (eg, carbamazepine, rifampin, phenytoin, and St. John's Wort). Consider alternative agents with less CYP3A induction. In vitro studies indicated that ibrutinib is not a substrate of P-glycoprotein (P-gp).

A list of common CYP3A inhibitors and inducers is provided in **Appendix B**. Please see table II for dose modification guidelines for ibrutinib if CYP3A inhibitors are required.

See below Table 2 for dose modification based on CYP3A inhibitor used.

Table 2. Dose modifications based on CYP3A inhibitor usage.

Co Administered Drug	Recommended Ibrutinib dose

 
Moderate CYP3A inhibitor
 
Voriconazole 200 mg twice daily
 
Posaconazole suspension 100 mg once daily, 100mg twice daily, or 200mg twice daily
 
	140mg once daily

 
Posaconazole suspension 200mg three times daily or 400mg twice daily
 
Posaconazole IV injection 300mg once daily
 
Posaconazole delayed release tablets, 300mg once daily.
 
	70 mg once daily
Other stronger CYP3A inhibitors	Avoid concomitant use

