### **11. Duration of Therapy and Criteria for Removal from Study**

In the absence of treatment delays due to adverse event(s) greater than 4 weeks from scheduled dose, combination treatment may continue for 2 years with 1 year of ibrutinib monotherapy or until one of the following criteria applies:

- Disease progression,
- Intercurrent illness that prevents further administration of treatment,
- Unacceptable adverse event(s),
- Patient decides to withdraw from the study, or
- General or specific changes in the patient's condition render the patient unacceptable for further treatment in the judgment of the investigator.

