## **22. Data and Safety Monitoring Plan (DSMP)**

Monitoring activities will be commensurate with the nature, size and complexity of the trial in accordance with institutional policies and will be determined after IRB and Data Safety Monitoring Board (DSMB) review of the protocol immediately prior to study activation. For this study we will utilize a Weill Cornell Medicine DSMB.

We will evaluate safety of combination therapy after 12 subjects have been enrolled onto the protocol and completed 8 weeks of combination induction therapy. The study team will review all subject data at this specified time point and provide a written report to the DSMB for review. Stopping rules will be employed in this study based on observed toxicities from monotherapy trials in subjects with multiple myeloma receiving daratumumab or WM subjects receiving monotherapy ibrutinib. For purposes of this safety analysis, each subject will be assessed individually and toxicities tabulated. Only toxicities occurring within the first 8 weeks of combination treatment will be considered for potential study termination.

In monotherapy daratumumab or ibrutinib studies, Grade 3 or greater non hematologic toxicities were rare with the most common event being pneumonia noted in 6% of subjects respectively for daratumumab and ibrutinib (data from prescribing inserts). Grade 3 or greater hematologic toxicities when restricted to anemia, thrombocytopenia, or neutropenia were noted in up to 20% of subjects treated with daratumumab monotherapy and up to 19% in subjects treated with ibrutinib monotherapy.

Based on these observed events we will stop the study if 5 of the first 12 subjects enrolled experience a Grade 3 or greater, toxicity (heme or non-heme) which leads to a study drug hold greater than 28 days or leads to either study drug discontinuation within the first two months of treatment. Any drug hold that occurs within the first 8 weeks but extends beyond the initial 8 week monitoring period will be followed for a full 28 days. For a toxicity to be included in this analysis, the toxicity must be considered due to the study drug per investigator assessment. Accrual will be held upon enrollment of the 12th evaluable subject until they have been observed through induction and the study team in consultation with the DSMB have made a determination regarding additional enrollment, this study hold is anticipated to last approximately 3 months.

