## Appendix B: Inhibitors and Inducers of CYP3A

Inhibitors of CYP3A are defined as follows. A comprehensive list of inhibitors can be found at the following website: <http://medicine.iupui.edu/clinpharm/ddis/main-table/>. The general categorization into strong, moderate, and weak inhibitors according to the website is displayed below.

Inhibitors of CYP3A	Inducers of CYP3A

Strong inhibitors:
 
indinavir nelfinavir ritonavir clarithromycin itraconazole ketoconazole nefazodone saquinavir suboxone telithromycin cobicistat beceprevir telaprevir troleandomycin posaconazole
 
Moderate Inhibitors:
 
aprepitant amprenavir atazanavir ciprofloxacin crizotinib darunavir/ritonavir dronedarone erythromycin diltiazem fluconazole grapefruit juice Seville orange juice verapamil voriconazoleb imatinib
	
carbamazepine efavirenz nevirapine barbiturates glucocorticoids modafinil oxcarbarzepine phenobarbital phenytoin pioglitazone rifabutin rifampin St. John's Wort troglitazone

Source: <http://medicine.iupui.edu/clinpharm/ddis/main-table/>

a. Based on PBPK simulations, up to 9.7-fold increase in AUC and 6.2-fold increase in  $C_{max}$  could be observed. If ibrutinib needs to be administered with posaconazole, 140 mg ibrutinib will be dosed.

b. Based on internal data, 140 mg ibrutinib dosed with voriconazole produces ibrutinib exposures similar to 560 mg ibrutinib dosed alone. Therefore, for this study, if ibrutinib needs to be administered with voriconazole, 140 mg ibrutinib will be dosed.

**Appendix C: Consensus-based uniform response criteria for WM developed by the International Workshop on WM ,updated in the Sixth IWWM and published by Owen et al.**

Response category Definition	
Complete response (CR)	Absence of serum monoclonal IgM protein by immunofixation Normal serum IgM level Complete resolution of extramedullary disease, i.e., lymphadenopathy and splenomegaly if present at baseline Morphologically normal bone marrow aspirate and trephine biopsy
Very good partial response (VGPR)	Monoclonal IgM protein is detectable ≥90% reduction in serum IgM level from baseline* Complete resolution of extramedullary disease, i.e., lymphadenopathy/splenomegaly if present at baseline No new signs or symptoms of active disease

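### The fixed ibrutinib restart doses in Section 12.4.2 are reductions only from 420 mg and are not reconciled with the 140 and 70 mg interaction doses in Table 2 (minor safety correction)

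*Combined protocol and SAP*

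**What the plan says.** Section 12.4.2 opens with a directive: "For toxicities outlined in Section 12.4 the following dose modifications are to be taken". After a first occurrence the subject restarts at the original dose level. The next step reads "Second Occurrence: Withhold ibrutinib until recovery to Grade 1 or less, restart at 280mg/day". The third occurrence leads to 140 mg/day and the fourth to discontinuation. The triggering toxicities in Section 12.4 are serious: Grade 4 hematologic toxicity, Grade 3 thrombocytopenia with bleeding, febrile neutropenia, and Grade 3 or higher non-hematologic toxicity with listed exceptions.

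Section 10.2 sets separate doses for drug interactions: "Dose modifications of ibrutinib are recommended when used concomitantly with posaconazole, voriconazole, and moderate CYP3A inhibitors". Its Table 2 gives 140 mg daily with a moderate CYP3A inhibitor, voriconazole or lower-dose posaconazole suspension, and 70 mg daily with the higher posaconazole doses. Other strong inhibitors are to be avoided.

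These subjects are not kept out at entry. Item 10 of Section 7.3 lists "Requires chronic treatment with strong CYP3A inhibitors" as an exclusion, with a washout provision, but says nothing about moderate inhibitors. Appendix B counts common drugs such as diltiazem, verapamil and fluconazole as moderate.

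Appendix B adds two footnotes. Footnote b states that "140 mg ibrutinib dosed with voriconazole produces ibrutinib exposures similar to 560 mg ibrutinib dosed alone". Footnote a says "If ibrutinib needs to be administered with posaconazole, 140 mg ibrutinib will be dosed", without the 70 mg level that Table 2 gives for higher posaconazole doses.

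**The concern.** Two dosing rules can apply to the same subject, and no section says which prevails. The toxicity steps are written as milligram amounts that make sense for someone starting at 420 mg. They do not depend on the dose the subject is taking when the toxicity occurs. Nothing in Sections 10.2, 12.4 or 12.4.2 or in Appendix B gives a toxicity step below an interaction dose.

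The wording does not settle the conflict safely. The Table 2 doses are described as recommended, whereas the 12.4.2 steps are stated as actions to be taken. The term original dose level is also unclear for a subject who began at 420 mg and was moved to a Table 2 dose when an inhibitor was added during the study.

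What is at stake is the dose given after a second serious toxicity to someone also taking an interacting drug. Safety of the combination is the primary objective, so the rules for responding to toxicity should be unambiguous.

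**Working it through.** **Inputs.** Standard dose 420 mg (Section 12.3). Restart steps of 280 mg at the second occurrence and 140 mg at the third (Section 12.4.2). Interaction doses of 140 and 70 mg (Section 10.2, Table 2). With voriconazole, 140 mg is similar to 560 mg alone (Appendix B, footnote b). The plan states no figure of its own to reproduce here.

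**Step 1: literal reading.** Ratio = restart dose / dose before the toxicities.

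| Starting dose | Second occurrence | Third occurrence |
|---|---|---|
| 420 mg | 280/420 = 0.67 | 140/420 = 0.33 |
| 140 mg | 280/140 = 2.0 | 140/140 = 1.0 |
| 70 mg | 280/70 = 4.0 | 140/70 = 2.0 |

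Both steps reduce the dose only from 420 mg. From either interaction dose, neither step goes below the starting point.

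**Step 2: Table 2 as a ceiling.** Restart dose = the smaller of the 12.4.2 step and the Table 2 dose. Doses in mg:

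| Subject | Start | After 1st | After 2nd | After 3rd | 4th |
|---|---|---|---|---|---|
| No inhibitor | 420 | 420 | 280 | 140 | stop |
| On 140 mg | 140 | 140 | 140 | 140 | stop |
| On 70 mg | 70 | 70 | 70 | 70 | stop |

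The dose never rises, but it never falls either. The subject without an inhibitor gets two reductions; the other two get none.

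**Step 3: exposure, voriconazole only.** Using footnote b as it stands, a subject held at 140 mg with voriconazole stays at an exposure similar to 560 mg alone after the second and third occurrences. The standard steps are 280 and 140 mg, so the ratios are 560/280 = 2 and 560/140 = 4. No scaling assumption is needed.

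If exposure is also assumed proportional to dose (factor 560/140 = 4), the literal 280 mg step corresponds to 280 × 4 = 1120 mg alone, or 1120/420 = 2.7 times the standard dose. A step to 70 mg corresponds to 70 × 4 = 280 mg alone, which equals the standard second step. The documents give no net exposure at the Table 2 dose for the other moderate inhibitors, so no figure is offered for them.

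**The case against.** **The rise is not the natural reading.** Section 12.4.2 is a step-down scheme, and nothing in it suspends Table 2 while the inhibitor continues. An investigator would probably not increase a dose after a second serious toxicity. This stands. A reader might infer that the protocol requires a dose escalation after toxicity; the documents do not support that as the only, or the likelier, meaning. What remains is that no sentence rules it out, and that the ceiling reading leaves no reduction.

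**The subject is not unmanaged.** Every occurrence requires a hold until recovery to Grade 1 or less. Section 11 ends treatment for unacceptable adverse events or on the investigator's judgment, and Section 22 lets the investigator discontinue a subject at any time. Changing the inhibitor is not prohibited. This also stands and limits the harm, but these provisions are discretionary and supply no dose step.

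**The label may cover it.** Section 13.2 says ibrutinib is used according to its FDA labeling. The label is not among the documents, so this cannot be checked. The protocol writes its own explicit steps and reproduces no label rule for this case.

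**Exposure may not be high.** The Table 2 dose is already lowered for the interaction, so a reader should not infer that every affected subject is over-exposed. The documents show net exposure only for voriconazole, where footnote b knowingly accepts a level similar to 560 mg. Even the 1120 mg-equivalent on the literal reading is below the 1400 mg/day at which Section 12.3.1 reports that no maximum tolerated dose was reached.

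**Conclusion.** The gap is real, and it lies in a stated rule rather than in missing detail. Section 12.4.2 gives doses that do not work for a subject on a Table 2 dose: a 2-fold or 4-fold rise at the second occurrence if taken literally, or no reduction before discontinuation at the fourth if Table 2 is kept as a ceiling. The dose arithmetic needs no assumption. The exposure comparison rests on footnote b and holds for voriconazole only; the equivalents for 70 and 280 mg also assume dose proportionality.

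The practical reach is small. A subject must be on a Table 2 inhibitor and have at least two qualifying toxicities, the second while still on the inhibitor. Few of the 24 subjects, possibly none, will meet this. The 70 mg case is rarer still, because Appendix B classes posaconazole as a strong inhibitor and chronic strong inhibitors are excluded at entry. A reader might infer that the primary toxicity proportion or its confidence interval is compromised; nothing in the documents supports that. This is a minor safety correction.

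**What to change.** Add to Section 12.4.2:

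1. While a Table 2 inhibitor is co-administered, the restart dose must never exceed the Table 2 dose, and original dose level then means that dose.
2. At a second occurrence, a subject on 140 mg restarts at 70 mg, which is already a Table 2 dose, or the inhibitor is replaced where possible. For a subject already on 70 mg, the investigator, with the sponsor, replaces the inhibitor or discontinues ibrutinib. A subject stepped down to 70 mg who has a third occurrence is then in the same position.
3. The subject returns to the standard dose for the number of occurrences so far (420 mg after none or one, 280 mg after two, 140 mg after three) only after the inhibitor has been stopped and washed out. Without the washout, a move from 70 to 280 mg would repeat the 4-fold step while inhibition may persist. The sponsor should set the interval; the protocol's only washout figure for inhibitors is the 14 days for strong ones at entry.
4. Discontinuation at the fourth occurrence stays for everyone.

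In Appendix B, correct footnote a to match Table 2: 140 or 70 mg according to the posaconazole dose.

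The cost is a few sentences and one footnote, with no added subjects, visits or procedures. The downside is earlier dose reduction or discontinuation in a few subjects. Existing limits would apply to them as usual. Section 11 allows combination treatment to continue only "In the absence of treatment delays due to adverse event(s) greater than 4 weeks from scheduled dose". Under Section 22, a drug-related Grade 3 or higher toxicity that "leads to a study drug hold greater than 28 days or leads to either study drug discontinuation within the first two months of treatment" counts toward the stopping threshold of 5 of the first 12 subjects.
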